# 6.4.2 Day 3 Visit: Cohort 2b

Cohort 2b I	Cohort 2b Day 3 Visit Procedures (straight to injection)		
Clinical		Update medical and medications history	
		Perform targeted physical exam	
		Identify/review/update adverse events	
Laboratory	Blood (PK	Collect blood for:	
	evaluation)	Hematology: CBC (WBC, RBC, hemoglobin, hematocrit, MCV, MCHC) with differential, ANC (absolute neutrophil count), and platelet count	
		• Chemistries: Creatinine, eGFR, CK, Direct bilirubin, Total bilirubin, BUN, AST, ALT, Lipase, Albumin	
		PK evaluation: Single sample	

\*If indicated and/or per local standard of care

# 6.4.3 Week 2 Visit: Cohort 2b

Cohort 2b V	Cohort 2b Week 2 Visit Procedures		
Behavioral a	nd Counseling	Provide contraceptive counseling*^	
Clinical		Update medical and medications history	
		Perform targeted physical exam	
		Identify/review/update adverse events	
Laboratory	Blood	Collect blood for:	
		Hematology: CBC (WBC, RBC, hemoglobin, hematocrit, MCV, MCHC) with differential, ANC (absolute neutrophil count), and platelet count	
		Chemistries: Creatinine, eGFR, CK, Direct bilirubin, Total bilirubin,	
		BUN, AST, ALT, Lipase, albumin	
		• HIV-1 RNA	
		PK evaluation: Single sample	

\*If indicated

## 6.4.4 Week 4 Visit: Cohort 2b

Cohort 2b	Cohort 2b Week 4 Visit Procedures		
Behavioral and Counseling		
 
Provide contraceptive counseling^
 
Administer participant acceptability/tolerability assessment based upon participant age, as specified in the IMPAACT 2036 MOP
 
	
 		Administer parent/caregiver acceptability/tolerability assessment	
Clinical		
 
Update medical and medications history
 
Perform targeted physical exam
 
Identify/review/update adverse events
 
	
Laboratory	Blood	
 
Collect blood for:
 
Hematology: CBC (WBC, RBC, hemoglobin, hematocrit, MCV, MCHC) with differential, ANC (absolute neutrophil count), and platelet count
 
Chemistries: Creatinine, eGFR, CK, Direct bilirubin, Total bilirubin, BUN, AST, ALT, Lipase, Albumin
 
HIV-1 RNA
 
PK Evaluation: Single pre-dose sample
 
	

^ For participants of childbearing potential.

^ For participants of childbearing potential.

	Blood or Urine	Pregnancy test
Study product		Prescribe, prepare, and administer injectable study products

^ For participants of childbearing potential.

## 6.4.5 Week 8, 12, and 16 Visits: Cohort 2b

Cohort 2b V	Neek 8, 12,	and 16 Visit Procedures
Behavioral a	ınd	Provide adherence counseling
Counseling		Provide contraceptive counseling^
_		Administer participant acceptability/tolerability assessment based upon participant age, as specified in the IMPAACT 2036 MOP
Clinical		Update medical and medications history
		Perform targeted physical exam
		Identify/review/update adverse events
Laboratory	Blood	Collect blood for:
		Hematology: CBC (WBC, RBC, hemoglobin, hematocrit, MCV, MCHC) with differential, ANC (absolute neutrophil count), and platelet count
		Chemistries: Creatinine, eGFR, CK, Direct bilirubin, Total bilirubin, BUN, AST, ALT, Lipase, Albumin
		• HIV-1 RNA
		PK evaluation (Week 12 only): Single pre-dose sample
	Blood or Urine	Pregnancy test^
Study produ	ct	Prescribe, prepare, and administer injectable study products

^ For participants of childbearing potential.

#### 6.4.6 Week 20 Visit: Cohort 2b

The in-depth interview (IDI) will be conducted with a subset of parents and caregivers at select sites, during the Week 20 visit window. The interview may be conducted in person or via telephone. The interview must be completed within the specified Week 20 window, but may be conducted as part of the regular study visit or can occur as a stand-alone visit, per site discretion and parent/caregiver preferences.

Cohort 2b V	Neek 20 V	isit Procedures
Behavioral a	ınd	Provide adherence counseling
Counseling		• Provide contraceptive counseling^
		Administer participant acceptability/tolerability assessment based upon participant age, as specified in the IMPAACT 2036 MOP
		Administer parent/caregiver acceptability/tolerability assessment
		• Conduct qualitative interview*
Clinical		Update medical and medications history
		Perform complete physical exam
		Identify/review/update adverse events
		• Perform an ECG
Laboratory	Blood	Collect blood for:
		• Hematology: CBC (WBC, RBC, hemoglobin, hematocrit, MCV, MCHC) with differential, ANC (absolute neutrophil count), and platelet count
		• Chemistries: Creatinine, eGFR, CK, Direct bilirubin, Total bilirubin, BUN, AST, ALT, Lipase, Albumin
		CD4 count and percentage
		• HIV-1 RNA

		
 
Store plasma for genotypic and phenotypic resistance testing
 
PK evaluation: Single pre-dose sample
 

	Blood or Urine	Pregnancy test^
Study produ	ct	Prescribe, prepare, and administer injectable study products

\*If indicated

#### 6.4.7 Weeks 24, 28, 32, 36, 40, 44 Visits: Cohort 2b

Week 44 is considered the study end visit for Cohort 2b participants that have continued receiving injections per schedule.

Cohort 2b V	Neek 24, 28	8, 32, 36, 40, 44 Visit Procedures
Behavioral a	ınd	Provide contraceptive counseling^
Counseling		• Provide adherence counseling (Week 44 only, and if indicated at all other visits)
		Administer participant acceptability/tolerability assessment based upon participant age, as specified in the IMPAACT 2036 MOP
		Administer parent/caregiver acceptability/tolerability assessment (Week 44 only)
Clinical		Update medical and medications history
		Perform complete physical exam (Week 44 only)
		Perform targeted physical exam (All other visits except Week 44)
		Identify/review/update adverse events
Laboratory	Blood	Collect blood for:
		Hematology: CBC (WBC, RBC, hemoglobin, hematocrit, MCV, MCHC) with differential, ANC (absolute neutrophil count), and platelet count
		• Chemistries: Creatinine, eGFR, CK, Direct bilirubin, Total bilirubin, BUN, AST, ALT, Lipase, Albumin
		• CD4 count and percentage (Week 44 only)
		• HIV-1 RNA
		PK evaluation (Weeks 28, 36, 44only): Single pre-dose sample
	Blood or Urine	Pregnancy test^
Study produ	ct	Prescribe, prepare, and administer injectable study products

^ For participants of childbearing potential.

# 6.5 Interim Injection Visit

For participants resuming injectable study products following oral bridging or in other rare circumstances, one or more interim visits may be required to appropriately reinitiate a participant on the dosing regimen or realign to the original injection visit schedule or dose. The CMC must be consulted prior to initiating oral bridging and prior to conducting an interim injection visit regarding clinical considerations, and injectable study product management and scheduling.

Interim injection visit procedures are provided below, and study data will be entered into eCRFs. Further details and guidance on scheduling and conducting interim injection visits are provided in the IMPAACT 2036 MOP.

^ For participants of childbearing potential.

Interim Injection Visit Procedures		Procedures
Behavioral a	nd	Provide adherence counseling*
Counseling		• Provide contraceptive counseling, if indicated^
Clinical		Update medical and medications history since last visit*
		Perform targeted physical exam*
		Identify/review/update adverse events*
Laboratory	Blood	Collect blood for:
		Hematology: CBC (WBC, RBC, hemoglobin, hematocrit, MCV, MCHC) with differential, ANC (absolute neutrophil count), and platelet count
		• Chemistries: Creatinine, eGFR, CK, Direct bilirubin, Total bilirubin, BUN, AST, ALT, Lipase, Albumin
		• HIV-1 RNA*
		PK evaluation: Single pre-dose sample*
	Blood or Urine	Pregnancy test^
Study produ	ct	Prescribe, prepare, and administer injectable study products

\*Perform prior to administration of injectable study products.

# 6.6 Long-Term Safety and Washout PK Follow-Up (LSFU) Visits

Participants who prematurely and permanently discontinue injectable study product, or participants who discontinue study product use (either oral or injectable study product) due to pregnancy, will be followed for an additional 48 weeks to assess long-term safety and washout PK of the study products. Additionally, participants who receive their injections at their final scheduled follow-up visit (Week 72 for Cohort 1, Week 48 for Cohort 2a, and Week 44 for Cohort 2b) but do not wish to continue the CAB LA + RPV LA regimen outside of the study will resume (non-study provided) ART and enter into the LSFU visit schedule. Participants will resume (non-study provided) oral cART as soon as possible, and within 4 weeks, or 8 weeks (±7 days), of discontinuing study product depending on the study product dosing regimen which was discontinued (i.e., O4W or O8W dosing regimen). The LSFU visits will be scheduled approximately 4, 8, 24, 36, and 48 weeks after the last injection, after which participants will exit the study. Participants who permanently discontinue study product (either oral or injectable study product) due to pregnancy will be followed for 48 weeks, based on the date of the positive confirmatory pregnancy test result. For participants who become pregnant during LSFU visits, the LSFU visits will continue as scheduled and not restart. All LSFU visit procedures will be conducted, with the exception that pregnancy testing will not be required for participants who are currently pregnant. See Section 8.2 for further details on management of pregnant participants and pregnancy outcome.

During LSFU, a single random PK sample will be collected at each visit as shown in the procedural tables below.

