# Residual concentrations and risk of resistance following discontinuation of CAB LA or RPV LA

Residual concentrations of CAB and RPV can remain in the systemic circulation for prolonged periods (more than 1 year in some cases) in participants who stop CAB LA or RPV LA treatment (e.g., for tolerability issues or treatment failure) (7).

Participants discontinuing a CAB LA + RPV LA regimen may therefore be at risk for developing HIV-1 resistance to CAB and/or RPV after discontinuing injectable therapy (7).

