Cohort 2 will consist of two groups, Cohort 2a and Cohort 2b, which will allow participants to choose between a regimen that includes an oral lead-in and one that does not. Participants enrolled in Cohort 2a will progress through two steps of study participation, as described above for Cohort 1. Cohort 2a participants will receive oral CAB + oral RPV (Step 1) through the Week 4b visit, followed by intramuscular injection doses of CAB LA + RPV LA from Week 4b (Step 2 entry) through Week 48, based upon the relevant weight band dosing regimens recommended at the time. Participants enrolled to Cohort 2b will skip the oral lead-in phase and receive both CAB LA + RPV

LA upon entry into the study and continuing through Week 44, based upon the relevant weight-band dosing regimens recommended at the time.

The decision to join Cohort 2a or Cohort 2b will be made by the potential study participant and/or the parent/legal guardian in consultation with the IoR or designee and other healthcare providers, as applicable. This choice will be made as part of the parental permission and informed assent process and must be confirmed prior to study entry; participants may not change their Cohort 2a or Cohort 2b group selection after enrollment.

Section 6.6 provides details for participants who will be followed for an additional 48 weeks on an adjusted follow-up schedule to assess long-term safety and washout PK of the study products, referred to as the LSFU visit schedule. This includes participants who prematurely permanently discontinue study product during the injection phase, participants who discontinue oral or injectable study product due to pregnancy, and participants who complete the injectable study product regimen, but do not wish to continue the CAB LA + RPV LA regimen outside of the study.

## 3.2 Dose-finding and Evaluability: Cohort 1

Cohort 1 will include a dose-finding phase to assess whether any dosing regimen modifications are indicated per weight band; this phase culminates in two separate interim analyses, as described below. Separate terms will be used in the study to describe the participants who will contribute to the dose-finding phase (dose-evaluable) and the participants contributing the accrual targets (evaluable):

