# 6.3.9 Weeks 28, 32, 36, 40, 44, 48, 52, 56, 60, 64, 68, 72 Visits: Step 2 – injection phase for Cohort 1 (through Week 72) and Cohort 2a (through Week 48 only)

Week 72 is considered the final scheduled follow-up visit for participants in Cohort 1 who wish to continue receiving the injections external to the study; Week 48 is the final scheduled follow-up visit for participants in Cohort 2a. See Section 6.8 for Study Exit considerations and Section 13.11 for more information regarding post-trial access to study drugs.

Behavioral and Counseling		
 
44, 48, 52, 56, 60, 64, 68, 72 Visit Procedures (Step 2 – injection phase)
 
Provide contraceptive counseling^
 
Provide adherence counseling (Week 48 only, and if indicated at all other visits)
 
Administer participant acceptability/tolerability assessment based upon participant age, as specified in the IMPAACT 2036 MOP
 
Administer parent/caregiver acceptability/tolerability assessment (Weeks 48 and 72 only)
 

Clinical		
 
Update medical and medications history
 
Perform complete physical exam (Weeks 48 and 72 only)
 
Perform targeted physical exam (All other visits except Weeks 48 and 72)
 
Identify/review/update adverse events
 

	Blood	
 
Collect blood for:
 
Hematology: CBC (WBC, RBC, hemoglobin, hematocrit, MCV, MCHC) with differential, ANC (absolute neutrophil count), and platelet count
 
Chemistries: Creatinine, eGFR, CK, Direct bilirubin, Total bilirubin, BUN, AST, ALT, Lipase, Albumin
 
CD4 count and percentage (Weeks 48 and 72 only)
 
HIV-1 RNA
 
PK evaluation (Weeks 32, 40, 48, 56, 64, and 72 only): Single pre-dose sample
 

	Blood or Urine	Pregnancy test^
Study product		Prescribe, prepare, and administer injectable study products

^ For participants of childbearing potential.

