## 13.11 Post-Trial Access to Study Drug

ViiV Healthcare Ltd and Janssen Research & Development LLC are committed to exploring all options to provide continued access to investigational product to participants deriving therapeutic benefit from CAB LA + RPV LA. Upon identification of a suitable option for access, participants who received CAB LA + RPV LA and who have successfully completed 72 weeks on study for Cohort 1, or 48 weeks/44 weeks for Cohorts 2a/2b, respectively, will be given the opportunity to continue to receive CAB LA + RPV LA. Additionally, both of the following conditions must be met for the participant to continue to receive CAB LA + RPV LA:

- there is evidence of continued clinical benefit for the participant;
- and such provision of CAB LA + RPV LA is permitted under local laws and regulations.

The investigator is responsible for ensuring that consideration has been given to the post-study care of the participant and for determining whether all parameters are met for an individual participant's post-study access to CAB LA + RPV LA or whether the participant should transition to local standard HIV care and treatment (See Section 6.8). Continued access to unapproved CAB LA + RPV LA will cease if the participant no longer exhibits a clinical benefit or if risks of continuing treatment outweigh benefits. Additionally, access will cease if the development of CAB LA + RPV LA is discontinued or market access becomes available.

The mechanism that will be used to provide post-trial access to study drug may be country-specific; additional details will be provided in the study-specific MOP.

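### Children who complete the injections enter washout follow-up according to whether they wish to continue, not whether they can obtain the drug, so a completer without access falls outside the 48-week LSFU schedule

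*Protocol*

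**What the plan says.** Section 6.6 gives three routes into LSFU. Two concern stopping before the schedule is complete: "Participants who prematurely and permanently discontinue injectable study product, or participants who discontinue study product use" because of pregnancy. The third is for children who receive their injections at the final scheduled visit (Week 72 in Cohort 1, Week 48 in Cohort 2a, Week 44 in Cohort 2b) but "do not wish to continue the CAB LA + RPV LA regimen outside of the study will resume (non-study provided) ART and enter" the LSFU schedule. Section 3.1 states the third route in the same terms, for children who complete the regimen "but do not wish to continue the CAB LA + RPV LA regimen outside of the study".

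On exit, Section 6.3.9 says "Week 72 is considered the final scheduled follow-up visit for participants in Cohort 1 who wish to continue receiving the injections external to the study". It adds, without a condition, that "Week 48 is the final scheduled follow-up visit for participants in Cohort 2a". Section 6.4.7 makes Week 44 the end visit for Cohort 2b, and Section 6.8 counts all three visits as scheduled completion.

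Section 13.11 does not promise supply. The manufacturers undertake to explore ways of providing it. "Upon identification of a suitable option for access, participants who received CAB LA + RPV LA" and who completed the schedule are to be offered continued treatment, provided that there is evidence of continued benefit and that local law permits it. The investigator judges whether this is met or the child should move to local standard care, and for that case the section refers to Section 6.8.

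**The concern.** The entry rule for completers asks about the child's wish. Section 13.11 shows that wish and supply can part company. A child who wants to continue but has no access route did not stop early and is not unwilling, so no route in Section 6.6 applies. That child has just received depot injections.

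The protocol's own risk summary (Section 1.2.5.1) says that residual drug can persist for more than a year in some cases and that stopping carries a risk of resistance. Objective 2.4.1 is to characterise safety and washout PK for 48 weeks after permanent discontinuation. Children who stop because supply is not available belong to that objective, but the visit schedule would not observe them routinely. The completers who do enter LSFU would be those who chose to stop, which is a selected group for a washout estimate.

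**Working it through.** The plan states no figure for this point, so there is none to reproduce. The check sets the governing sections side by side and adds two small calculations.

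**1. Does any LSFU route cover a completer who wishes to continue but has no access?**
- Premature permanent discontinuation (3.1, 6.6): no, the schedule was completed.
- Pregnancy (3.1, 6.6): only if the child is pregnant and stops for that reason.
- Completed and does not wish to continue (3.1, 6.6): no, the child does wish to continue.

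**2. Where is the child sent instead?** Sections 6.3.9, 6.4.7 and 6.8 end participation at Week 72, 48 or 44 with no access condition. Section 13.11 foresees children who do not meet its conditions and points to Section 6.8, not 6.6. The schema and Figure 1 say only that participants who meet criteria enter LSFU, and add no access criterion.

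**3. What is lost?** LSFU has visits at 4, 8, 24, 36 and 48 weeks after the last injection (6.6), and 48 × 7 = 336 days (6.6.2). Each visit collects safety laboratory tests, HIV-1 RNA and a PK sample. The child in question has 0 of these 5 visits. Section 6.8 requires one contact within 4 weeks of exit to confirm transition of care. It carries no samples, is not expected on the eCRF, and reaches 28/336 = 8% of the way into the window.

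**4. What still applies after the final visit?**
- Section 6.7 recalls any participant with HIV-1 RNA of 200 copies/mL or more after enrollment, 2 to 4 weeks later, for viral load, resistance plasma and PK. HIV-1 RNA is drawn at Weeks 72, 48 and 44. Confirmed failure in the injection phase leads to LSFU (8.3). The list of reasons to postpone exit in 6.8.1 names only LSFU Week 48 results, so this recall rests on the general wording of 6.7.
- Adverse events are to be followed to resolution or stabilisation, and children with a Grade 3 or higher event at the last visit stay on study for up to 28 days (8.1).
- Pregnancy postpones exit (6.8.1, 8.2).

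**5. What do the objective and analysis cover?** Objective 2.4.1 and the Section 9.6.3 estimate refer to 48 weeks after permanent discontinuation of the injectables. Neither is restricted by the reason for stopping.

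**6. Residual drug, for illustration only.** Section 1.2.2 gives an apparent RPV LA half-life of 200 days in adults. With first-order decline, the fraction remaining at day t is 0.5^(t/200):
- day 28: 0.5^(28/200) = 0.91
- day 336: 0.5^(336/200) = 0.5^1.68 = 0.31

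Section 1.3.3 notes that absorption from muscle could be faster in children. If the half-life were half as long, the day-336 fraction would be the square, 0.312² = 0.10. The entry-rule gap does not depend on this figure.

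**The case against.** The strongest reply is that the gap is one of wording. A sensible site might treat a child without access as not continuing and enter that child into LSFU. Section 6.8 asks for transition planning before the exit visit, and 13.11 leaves country-specific access details to the study manual. Neither the manual nor the consent forms are at hand, and either may settle the matter. This stands as a limit on certainty, but Sections 3.1, 6.3.9, 6.6 and 6.8 set entry and exit in the protocol itself, and the pointer in 13.11 leads to exit. A manual should not have to overrule them.

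Four stronger readings are tempting, and the documents do not support them.
- **These children leave with no further data at all.** Recall for viral load, adverse event follow-up and pregnancy all remain. What is lost is routine follow-up in suppressed, event-free completers.
- **Failing any condition in 13.11 opens the gap.** Lack of benefit is largely caught earlier: virologic failure, specified adverse events and an investigator's judgement of detriment all lead to permanent discontinuation (8.3, 8.5), and during the injection phase that means LSFU. The main remaining cases are no access route and local law.
- **Sites without access would be missing from the washout data.** Their early stoppers, pregnancies and unwilling completers still enter LSFU. Only one subgroup would be absent.
- **The expedited reporting period in 7.3.4 must be extended.** It already runs to LSFU Week 48 for a child in LSFU.

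It is also fair to say that 2.4.1 is an Other objective, that 9.6.3 is descriptive, and that nothing in the protocol shows lack of access to be related to washout PK or late safety.

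**Conclusion.** The concern holds as a gap in the LSFU entry rule for completers. Followed literally, Sections 3.1, 6.3.9, 6.4.7, 6.6, 6.8 and 13.11 send a completer who wishes to continue but has no access to study exit at a final injection visit. That child misses 5 of 5 routine LSFU visits over 336 days, subject to the three exceptions above.

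The number affected is not given. It ranges from none, if access is secured everywhere, to every completer who wishes to continue in a country with no route. No primary or secondary objective depends on it. The residual-drug fraction (about 31% of the RPV level at 336 days) assumes that first-order decline and the adult half-life apply to children; it illustrates that a tail exists and does not measure the loss. The point merits a low-cost correction because the protocol itself flags the tail as a resistance risk and already has a schedule to observe it.

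**What to change.** Reconcile Sections 3.1, 6.3.9, 6.4.7, 6.6, 6.8 and 13.11 so that LSFU entry for completers is defined by outcome: any child who receives final-visit injections and does not go on to receive CAB LA + RPV LA outside the study, whatever the reason. In 13.11, point children who do not qualify to 6.6 as well as 6.8. Record on an eCRF whether access was confirmed, at or before the existing 4-week contact. Section 7.3.4 needs no change.

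The cost is amendment wording, one eCRF item, and the existing LSFU visits for children without access. No treatment rule changes.
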